8.2 Formulation

mRNA-1273 is provided as a sterile liquid for injection, white to off white dispersion in appearance, at a concentration of 0.2 mg/ml. Please refer to letter of authorization (LOA) from to cross-reference the drug master file (DMF).

8.3 Packaging and Labeling

Each of the study products will be labeled according to manufacturer specifications and include the statement “Caution: New Drug Limited by Federal Law to Investigational Use.” Sterile empty vials will be provided with latex-free stoppers.

8.4 Supply of Study Drug at the Site

mRNA-1273 will be stored as per manufacturer guidelines, dispensed, and accounted for by the investigational pharmacy.

8.4.1 Dosage/Dosage Regimen

Investigational product mRNA-1273 will be administered via intramuscular injection (IM) at three doses: standard-dose (50 ug), mid-dose (100 ug) or high-dose (200 ug).

Table 2: Dosing and Administration

Group	Sample Size	Dose	Route	Frequency
1 Standard	20	50 ug	IM	Day 1
2 Mid-dose	20	100 ug	IM	Day 1
3 High-dose	20	200 ug	IM	Day 1

8.4.2 Dispensing

Investigational product mRNA-1273 will be received at 0.2 mg/ml concentration and dispensed by the investigational pharmacy undiluted at three dosages: 50 ug (0.25 ml), 100 ug (0.5 ml) and 200 ug (1 ml).

8.4.3 Administration Instructions

Each dose will be administered via IM injection into the deltoid muscle on Day 1.

8.5 Supply of Study Drug at the Site

Study drug will be supplied by Moderna and stored at the UCLA investigational pharmacy as per manufacturer guidelines, dispensed, and accounted for by the investigational pharmacy.

8.5.1 Storage

Vaccine mRNA-1273 will be stored at 2° to 8°C (35.6° to 46.4°F) at clinical sites before preparation and vaccination. No dilution will be required. Doses could be held in syringes for up to 8 hours at room temperature before administration.

The number of study drug dispensed will be recorded on the Investigational Drug Accountability Record. The UCLA Clinical & Translational Science Institute - Office of Regulatory Affairs (CTSI ORA) will verify these documents throughout the course of the study.

8.6 Measures of Treatment Compliance

Not applicable

9 STUDY PROCEDURES AND GUIDELINES

A Schedule of Events representing the required testing procedures to be performed for the duration of the study is diagrammed in Appendix 1.

Prior to conducting any study-related activities, written informed consent and the Health Insurance Portability and Accountability Act (HIPAA) authorization must be signed and dated by the participant or participant's legal representative. If appropriate, assent must also be obtained prior to conducting any study-related activities.

9.1 Clinical Assessments

9.1.1 Concomitant Medications

Based on inclusion criteria, participants will be required to be on a regimen of triple immunosuppression including prednisone, mycophenolate mofetil (minimum 250 mg bid) or mycophenolate sodium (minimum 180 mg bid), and tacrolimus at the Day 1 study visit. Participants receiving IVIG or augmented immunosuppression for treatment of acute rejection, antibody mediated rejection or chronic rejection will be excluded from the study.

9.1.2 Demographics

Demographic information will be recorded at enrollment including race, ethnicity, sex, age, BMI, medication history, co-morbidities including cardiovascular disease, risk factors for cardiovascular disease, and immunosuppressive agents.

9.1.3 Medical History

Relevant medical history, including history of current disease, other pertinent respiratory history, and information regarding underlying risk factors will be recorded at screening.

9.1.4 Physical Examination

A complete physical examination will be performed by either the investigator or a sub-investigator who is a physician or a qualified member (NP) of the study team at Day 1. Qualified members of the study team (MD, NP, RN and PA) will perform a symptom directed physical exam on Days 7 and 30. New abnormal physical exam findings will be documented and will be followed by a physician or other qualified staff at the next scheduled visit.

9.1.5 Vital Signs

Body temperature, blood pressure, pulse oximetry, and respiratory rate will be performed and recorded.

9.1.6 Adverse Events

Information regarding occurrence of adverse events will be captured throughout the study. Duration (start and stop dates and times), severity/grade, outcome, treatment and relation to study drug will be recorded on the case report form (CRF).

9.2 Clinical Laboratory Measurements

9.2.1 Research Labs

Blood will be obtained and sent to the research lab for:

1. Total immunoglobulins: IgG, IgA, IgM.
2. Anti-RBD, anti-spike binding and neutralizing antibody levels
3. PBMCs collected for cellular response assays including flow cytometry with intracellular staining.
4. Whole blood collected for cellular response assays.
5. Troponin / CK and cytokines for storage on Days 0, 7 and 30.

9.2.2 Clinical Labs

The following may be checked for any unscheduled visits: Complete blood count with differential, comprehensive metabolic panel, tacrolimus / sirolimus level, C-reactive protein, erythrocyte sedimentation rate (ESR), total immunoglobulins (IgG, IgA, IgM), anti-RBD, anti-spike and neutralizing antibody levels, PBMCs collected for cellular response assays including flow cytometry with intracellular staining, whole blood collected for cellular response assays, troponin / CK, cytokines, PT, PTT, INR (16 mL of venous blood).

10 EVALUATIONS BY VISIT

10.1 Screening/Enrollment Day -30 to 0 (Phone)

1. Pre-screen participants via chart review using HIPAA waiver.
2. Invite eligible participants by phone to participate in study.
3. A qualified member of the study team will review study and provide ICF form. Participants will be asked to sign consent at Visit 1 prior to initiating any study-related procedures.
4. Assign the participant a unique screening number.

10.2 Visit 1 Day 1 (Clinic): Booster Vaccine Day

1. For participants who meet inclusion/exclusion criteria, the investigator team will again review the study with the participant (or participant's legal representative) in person and obtain written informed consent and HIPAA authorization.
2. Record demographic data.
3. Record medical history.
4. Review of birth control history with female participants of childbearing potential (<1 year since start of menopause).

5. For women of childbearing potential, counsel participants to use adequate birth control methods required during the trial to avoid pregnancy.
6. For women of childbearing potential, urine pregnancy test will be checked prior to study drug administration on Visit 1 (Day 1).
7. Confirmation participants meet all inclusion criteria and no exclusion criteria review.
8. Review pre-study concomitant medications and therapies and record on the appropriate CRF.
9. Review of influenza and any all 2019-CoV vaccinations or other experimental coronavirus vaccines.
10. Vital signs (HR, BP, temperature, oximetry), and height and weight for determination of BMI.
11. Full physical exam will include assessments of the following organs and organ systems: skin, head, ears, eyes, nose, and throat (HEENT), neck, lungs, heart, liver, spleen, abdomen, extremities, lymph nodes (axillary and cervical), and nervous system.
12. Obtain blood samples for baseline: Total immunoglobulins (IgG, IgA, IgM), anti-RBD, anti-spike binding and neutralizing antibody levels, PBMCs collected for cellular response assays including flow cytometry with intracellular staining, whole blood collected for cellular response assays, troponin / CK and cytokines for storage.
13. Confirm group assignment: standard-dose, mid-dose or high-dose group.
14. Inform participants of their designated dose.
15. Administration of booster vaccine.
16. Participants will be observed for 30-minutes post injection administration.
17. Dispense daily diary of symptoms for first 7 days after injection dispensed to participant measuring FDA Toxicity Grading Scale and adverse events.

10.3 Visit 2 Day 3 +/-1 Day (Phone – 2 days post booster):

1. All participants will complete a daily diary of solicited and unsolicited AEs from the vaccination until 7 days post-vaccination. Reactogenicity will be measured by the occurrence of solicited injection site and systemic reactions for the first 7 days post-vaccination utilizing the FDA Toxicity Grading Scale.
2. Participants will be contacted by telephone to query for safety events and review daily diaries. Based on the information collected, participants may be asked to return to the clinic for evaluation for an unscheduled visit.
3. Review daily diaries, AEs (solicited and unsolicited), SAEs, AESIs and MAAEs.
4. Participants will contact their primary care doctor, lung transplant pulmonologist or study principal investigator with any SAEs, AESIs or MAAEs.

10.4 Visit 3 Day 7 +/-2 Days (Clinic Visit – 6 days post booster):

1. Vital signs (HR, BP, temperature, oximetry), and height and weight for determination of BMI.
2. Symptom-directed (targeted) physical exam. Targeted physical examinations should also include an assessment for signs suggestive of AEs and AESIs. Interim or unscheduled physical examinations will be performed at the discretion of the PI or appropriate sub-investigator, if necessary, to evaluate AEs or abnormal clinical laboratory test results.
3. Obtain blood samples for follow-up: Total immunoglobulins (IgG, IgA, IgM), anti-RBD, anti-spike binding and neutralizing antibody levels, PBMCs collected for cellular response assays including flow cytometry with intracellular staining, whole blood collected for cellular response assays, troponin / CK and cytokines for storage.

5. Review daily diaries, AEs (solicited and unsolicited), SAEs, AESIs and MAAEs.

10.5 Visit 4 Day 30 +/- 7 Days (Clinic – 29 days post booster):

1. Vital signs (HR, BP, temperature, oximetry), and height and weight for determination of BMI.
2. Symptom-directed (targeted) physical exam. Targeted physical examinations should also include an assessment for signs suggestive of AEs and AESIs. Interim or unscheduled physical examinations will be performed at the discretion of the PI or appropriate sub-investigator, if necessary, to evaluate AEs or abnormal clinical laboratory test results.
3. Obtain blood samples for follow-up: Total immunoglobulins (IgG, IgA, IgM), anti-RBD, anti-spike binding and neutralizing antibody levels, PBMCs collected for cellular response assays including flow cytometry with intracellular staining, whole blood collected for cellular response assays, troponin / CK and cytokines for storage.
4. Review daily diaries, AEs (solicited and unsolicited), SAEs, AESIs and MAAEs.

10.6 Visit 5 Day 90 +/- 7 Days (Phone – 89 days post booster):

1. Participants will be contacted by telephone to query for safety events. AEs (solicited and unsolicited), SAEs, AESIs and MAAEs will be reviewed. Based on the information collected, participants may be asked to return to the clinic for evaluation.

10.7 Visit 6 Day 180 +/- 7 Days (Phone – 179 days post booster): End of study

1. Participants will be contacted by telephone to query for safety events. AEs (solicited and unsolicited), SAEs, AESIs and MAAEs will be reviewed. Based on the information collected, participants may be asked to return to the clinic for evaluation.

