5 CRITERIA FOR EVALUATION

5.1 Primary Safety Endpoint

Safety will be measured by the frequency and grade of solicited and unsolicited adverse events (AEs), SAEs, AESIs and MAAEs. Reactogenicity will be measured by the occurrence of solicited injection site and systemic reactions.

1. Frequency and grade of each solicited local and systemic reactogenicity AE will be recorded on a daily diary using the FDA Toxicity Grading Scale and collected from Day 1 until Day 7.
2. Frequency and grade of each unsolicited AEs will be recorded on a daily diary and collected from Day 1 until Day 30.
3. Frequency of any SAEs, AESIs and MAAEs will be collected from Day 1 until Day 180.

Simple descriptive statistics will be used to summarize toxicities in terms of type, severity and minimum or maximum values for laboratory measures, time of onset, duration, and reversibility or outcome. Tables will be created to summarize these toxicities and side effects. Safety Analyses will be performed on the Safety Analysis Set.

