6.2 Inclusion Criteria

1. All adult lung transplant recipients (age ≥ 18 at the time of consent) who received all of their COVID-19 vaccines after lung transplantation.
2. Received three or four doses of either the Moderna mRNA-1273 or Pfizer BNT162b2 vaccine with the last dose received at least 4 months prior to study enrollment.
3. Currently receiving standard regimen of three drug immunosuppression with prednisone, tacrolimus and mycophenolate mofetil (minimum 250 mg bid) or mycophenolate sodium (minimum 180 mg bid).

4. Agrees not to receive other investigational agents for prophylaxis against COVID-19 including Evusheld monoclonal antibodies for at least 30 days after the study vaccine.
5. Understands and agrees to comply with the study procedures and provides written informed consent.
6. Is in stable health without any new or worsening medical conditions in the opinion of the Investigator.
7. Female participants of childbearing potential (<1 year since start of menopause) may be enrolled in the study if the participant fulfills all the following criteria:
 - a. Has a negative pregnancy test at Visit 1 Day 1.
 - b. Has practiced adequate contraception or has abstained from all activities that could result in pregnancy for at least 28 days prior to the first injection (Day 1).
 - c. Has agreed to continue adequate contraception or practice abstinence through 3 months following the booster injection (Day 90).
 - d. Is not currently breastfeeding.
 - e. Adequate female contraception is defined as consistent and correct use of a Food and Drug Administration (FDA) approved contraceptive method in accordance with the product label. For example:
 - i. Barrier method (such as condoms, diaphragm, or cervical cap) used in conjunction with spermicide
 - ii. Intrauterine device
 - iii. Prescription hormonal contraceptive taken or administered via oral (pill), transdermal (patch), subdermal, or IM route
 - iv. Sterilization of a female participant's monogamous male partner prior to entry into the study
 - v. Note: periodic abstinence (e.g., calendar, ovulation methods) and withdrawal are not acceptable methods of contraception.

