11 ADVERSE EXPERIENCE REPORTING AND DOCUMENTATION

11.1 Adverse Events

An adverse event (AE) is any untoward medical occurrence in a clinical investigation of a participant administered a pharmaceutical product and that does not necessarily have a causal relationship with the treatment. An AE is therefore any unfavorable and unintended sign (including an abnormal laboratory

finding), symptom or disease temporally associated with the administration of an investigational product, whether or not related to that investigational product. Any medical condition that is present at the time that the subject is screened will be considered as baseline and not reported as an AE. However, if the severity of any pre-existing medical condition increases, it will be recorded as an AE.

AEs can be further divided into solicited AEs and unsolicited AEs. Solicited AEs are those for which the study team will specifically query the subject whether they occurred. Unsolicited AEs are those events that the subject report occurring without being queried about the specific event.

A suspected adverse event is one for which there is a ‘reasonable possibility’ that the drug caused the adverse event. A ‘reasonable possibility’ means there is evidence to suggest a causal relationship between the drug and the adverse event, but implies a lesser degree of certainty about causality compared with an adverse event. An unexpected AE is one of a type not identified in nature, severity, or frequency in the current Investigator’s Brochure or of greater severity or frequency than expected based on the information in the Investigator’s Brochure. All AEs will be assessed for severity and relationship to study intervention (Tables 3 and 4). Suspected, Unexpected, Serious Adverse Reactions (SUSAR) is an adverse event where a causal relationship with the study drug is at least possible but not listed in the Investigator Brochure (IB), Package Insert, and/or Summary of Product Characteristics and includes any of the following: suspected AE, unexpected AE and serious adverse experience (SAE). Episodes of myocarditis or pericarditis occurring in temporal association with vaccination will be reported as a SUSAR. Medically attended adverse event (MAAE) is defined as hospitalization, an emergency room visit or an otherwise unscheduled visit to or from medical personnel for any reason.

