Frequency and grade of each solicited AE (local and systemic reactogenicity) will be collected until Day 7 using the FDA Toxicity Grading Scale to be recorded on a daily diary. Frequency and grade of each unsolicited AEs will be collected until Day 30. Frequency of any SAEs, AESIs and MAAEs will be collected until Day 180. After Day 30 through the end of study on Day 180, only SAEs, AESIs and MAAEs will be reported as AEs. All AEs, solicited and unsolicited, will be captured on the appropriate CRF. Information to be collected for AEs includes event description, date of onset, assessment of severity, relationship to study product and alternate possible etiology, date of resolution, seriousness, and outcome. AEs occurring during the study-collection and reporting period will be documented appropriately regardless of relationship. AEs will be followed to resolution or stabilization.

Solicited Adverse Events:

Solicited AEs are anticipated local and systemic AEs for which consistent collection of information is desired. Study clinicians will follow and collect resolution information for any reactogenicity symptoms that are not resolved within 7 days. Solicited AEs (i.e., reactogenicity) will be collected using a daily diary and recorded on the appropriate CRF from the time of the vaccination until 7 days post vaccination (Days 1-7). For this study, solicited AEs will be defined and graded as follows (Tables 3):

Table 3: Solicited Adverse Reactions and Grading

Phase I/II, Open-label Dose-finding Trial of High-Dose mRNA-1273 Booster for Lung Transplant Recipients
Confidential

Reaction	Grade 0	Grade 1	Grade 2	Grade 3	Grade 4
Injection site pain	None	Does not interfere with activity	Repeated use of over-the-counter pain reliever > (greater than) 24 hours or interferes with activity	Any use of prescription pain reliever or prevents daily activity	Requires emergency room visit or hospitalization
Injection site erythema (redness)	< (less than) 25 mm or < 2.5 cm	25 - 50 mm or 2.5 - 5 cm	51 - 100 mm or 5.1 - 10 cm	> 100 mm or > 10 cm	Necrosis or exfoliative dermatitis (severe skin rash causing skin discoloration or peeling)
Injection site swelling/induration (hardness)	< 25 mm or < 2.5 cm	25 - 50 mm or 2.5 - 5 cm	51 - 100 mm or 5.1 - 10 cm	> 100 mm or > 10 cm	Necrosis (severe swelling with skin discoloration, blistering, or peeling)

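### Six subjective systemic solicited symptoms get no grade before the injection, so the plan's severity-increase rule has no recorded starting grade and stable chronic symptoms can be recorded as reactogenicity

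*Combined protocol and SAP*

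**What the plan says.** - **Endpoint.** Section 5.1: "Reactogenicity will be measured by the occurrence of solicited injection site and systemic reactions". Section 14.3 adds severity. Neither section makes a reaction conditional on change from baseline or on relatedness.
- **Instrument.** Section 5.1: "Frequency and grade of each solicited local and systemic reactogenicity AE will be recorded on a daily diary", on the FDA toxicity scale, Days 1 to 7. Section 11.1 starts this collection at vaccination. Table 3 grades the subjective items by present level, from none, through no and some interference with activity, to preventing daily activity and emergency care.
- **Order of Visit 1 (Section 10.2).** History, vital signs, full examination and bloods come first. Item 14 tells participants their dose, item 15 is the injection, item 16 the observation, and item 17 reads "Dispense daily diary of symptoms for first 7 days after injection dispensed to participant measuring FDA Toxicity Grading Scale and adverse events". Appendix 1 has no adverse event, symptom or diary review in the Visit 1 column.
- **Baseline rule (Section 11.1).** "Any medical condition that is present at the time that the subject is screened will be considered as baseline and not reported as an AE". It continues: "However, if the severity of any pre-existing medical condition increases, it will be recorded as an AE".
- **Eligibility (Section 6.2, item 6).** "Is in stable health without any new or worsening medical conditions in the opinion of the Investigator". A chronic symptom that is stable does not fail this criterion.

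**The concern.** The baseline rule compares two severities. For headache, fatigue, myalgia, arthralgia, nausea/vomiting and chills, the plan records only the later one. Every participant is a lung transplant recipient on three immunosuppressants, so some may arrive with long-standing symptoms of this kind. Someone with everyday fatigue that interferes somewhat with activity would truthfully enter grade 2 on each diary day. Whether this becomes a grade 2 systemic reaction then depends on a retrospective judgement by staff who know the dose.

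Reactogenicity is half of the primary objective, and its analysis is descriptive, so the tabulated rates are themselves the result. If stable symptoms enter them, each group's absolute rate is too high and the differences between doses look smaller than they are.

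**Working it through.** **The plan's own figures.** None is given for reactogenicity. The only computed design figure is 15 per group in Section 14.6, for the secondary log10 IgG comparison. It reproduces: difference 0.91 - 0.23 = 0.68, SD 0.63, two-sided 0.05, 80% power, exact two-sample t-test gives 14.5, rounded up to 15. The present point does not affect it.

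**Which Table 3 items lack a pre-dose value.** Table 3 has twelve items.
- Injection-site pain, redness and swelling: little need for a baseline.
- Fever: temperature is taken before the dose, so a baseline grade can be derived.
- Rash and axillary swelling: skin and axillary nodes are examined, but not graded.
- Headache, fatigue, myalgia, arthralgia, nausea/vomiting, chills: no pre-dose grade anywhere. These six are the point.

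**What can stand in for the missing grade.**
1. Medical history shows that a condition exists, not its Table 3 level. Its timing is also inconsistent: Section 9.1.3 places it at screening, while Section 10.2 and Appendix 1 place it at Visit 1. Screening in Section 10.1 is a chart review and phone contact up to 30 days earlier.
2. Onset date and alternative cause are collected for each event (Section 11.1). They can reveal that a symptom is old, but not whether it has worsened.
3. Causality (Table 5) reserves the Unrelated category for events where this is certain. Possibly allows an event that fits the expected timing and pattern even when other factors could easily explain it. Long-standing fatigue entered after vaccination fits that category readily.

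**Size, under a stated assumption.** Let p be the true vaccine-induced rate in a dose group. Let b be the share with an unrelated stable symptom that still reaches the count after those checks, independent of p and equal across groups. The documents give no value for b.

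- Recorded rate = 1 - (1-p)(1-b), an inflation of b(1-p).
- Recorded contrast = [1 - (1-p2)(1-b)] - [1 - (1-p1)(1-b)] = (p2 - p1)(1-b).

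| assumed b | contrast retained, 1-b | recorded rate if p = 46% |
|---|---|---|
| 10% | 90% | 51.4% |
| 20% | 80% | 56.8% |
| 30% | 70% | 62.2% |
| 40% | 60% | 67.6% |

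For example, at b = 20%: 1 - 0.54 × 0.80 = 0.568. The 46% is the rate of any systemic reaction after the third dose in lung transplant recipients (Section 2), used here only to put a number into the formula. As an observed rate it may already contain background symptoms. The factor 1-b does not depend on it.

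**The case against.** The other side has substance, and it limits the point in five ways.

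- **The plan does not direct that chronic symptoms be counted.** A reader might infer that everyday fatigue automatically becomes a reaction. Section 11.1 says the reverse: baseline conditions are not adverse events. The gap is that the rule lacks a starting grade and is not carried into the endpoint definition.
- **The rule is not unusable.** History, onset dates, diary review with the participant on Days 3 and 7, and exclusion 9 (conditions that could interfere with safety assessment or interpretation) all give partial control. Exclusion 7 removes acute illness and fever. What they do not give is a severity to compare with.
- **The gap does not reach all of Table 3.** It concerns six of twelve items.
- **A bias for or against one dose does not follow.** In the two randomised cohorts (54 of 60 participants, each with concurrent 50 ug controls) background symptoms are balanced in expectation. The Safety Analysis Set also holds six non-randomised participants, and mid- and high-dose recipients are not randomised against each other, but the documents do not show a bias in any direction.
- **Background symptoms are unlikely to halt the trial by themselves.** Section 12.3 item 2 needs three or more grade 3 reactions in one dose group, each lasting at least 48 hours and judged at least possibly related, and it leads to a pause with DSMB review. If every background grade 3 symptom of that duration were judged possibly related, with one per participant, three or more among 18 would occur with probability 0.5%, 5.8% or 26.6% at assumed prevalences of 2%, 5% or 10%. The higher prevalences are hard to reconcile with the stable-health criterion and exclusion 9.

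It is also tempting to read the 46% and 80% in Section 2 as two dose rates. They compare transplant recipients with healthy recipients, so they cannot size a dose contrast.

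**Conclusion.** The point stands in limited form. For six subjective systemic symptoms the plan records no pre-dose grade, so its own severity-increase rule has nothing on the same scale to measure from. Stable chronic symptoms can be recorded as reactogenicity, which would inflate absolute rates and dilute dose contrasts by the factor 1-b. At assumed background shares of 10% to 40% that is a loss of 10% to 40% of any true contrast. This rests on independence, on an equal background in each group, and on values of b that no document supplies; effective onset and causality review would make b smaller.

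The plan already uses the principle elsewhere: Appendix 3 grades haemoglobin by change from baseline as well as by level, and adjusts some laboratory limits for this population. Table 3 comes from a healthy-volunteer scale and has no such step. The change is worth making before enrolment because the grade cannot be reliably recovered after dosing. It is a cheap improvement in measurement and does not mean that the primary endpoint fails.

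**What to change.** 1. At Visit 1, before item 15 and preferably before item 14, have the participant complete the Table 3 systemic-symptom page once, for the preceding 24 hours. Add it to Section 10.2 and to the Visit 1 column of Appendix 1.
2. In Sections 5.1 and 14.3, tabulate by dose the reactions whose maximum post-dose grade exceeds the pre-dose grade, beside the raw diary frequency. Keep both: a maximum over seven days set against a single reading will still flag some fluctuating chronic symptoms.
3. Show the DSMB the pre-dose grade with any solicited reaction it reviews. The halting rules stay as written.

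Cost: a few minutes at an existing visit, one CRF page and one table column. No added visit, procedure or staff.
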